## **Significance**

The Center for Disease Control (CDC) released guidelines in 2016 on narcotic prescribing for chronic pain due to growing concern regarding narcotic abuse. The guidelines suggest minimizing narcotic use for acute pain as a strategy to decrease the conversion to long-term use. With more than 600,000 hysterectomies performed annually in the United States, there is a dire need for establishing alternative pain therapies after surgery. We aim to determine the effectiveness of abdominal ice pack use on decreasing narcotic use postoperatively. Ice pack use on the abdominal wall likely inhibits visceral afferent pain fibers via somatic afferent nerve cross-talk. Importantly, patient-reported narcotic use has not been well documented so we will plan to accurately document post-discharge use by residual pill counts.

## **Innovation**

Our goal is to quantify narcotic use after hospital discharge following hysterectomy, and evaluate the effectiveness of abdominal ice packs as low cost adjuncts for pain control. We hope to demonstrate the feasibility and effectiveness of ice packs for pain reduction as measured by postoperative narcotic use, patient pain scores, and patient subjective assessment of acceptability. Abdominal ice packs have yet to be studied as pain control adjuncts in laparoscopic surgery, thus this approach is novel.

We will assess narcotic use after discharge by collecting unused pills from patients. This is an innovative approach to document post-discharge narcotic use after laparoscopic hysterectomy, for which there is an absence of published data. Data on narcotic use after hysterectomy may become a basis for future recommendations on appropriate narcotic prescribing following hysterectomy. Demonstrating a clinically significant narcotic use reduction or pain reduction with abdominal ice pack therapy would likely lead to widespread adoption of the practice within gynecology.

## **ABSTRACT**

### **Background**

Hysterectomy is one of the most common procedures performed on women in the United States, with approximately 600,000 performed annually. The Center for Disease Control (CDC) released guidelines in 2016 on narcotic prescribing for chronic pain due to growing concern regarding narcotic abuse. The guidelines suggest parameters for narcotic prescribing for acute pain due to its relationship to long-term narcotic use, with a focus on limiting the amount of narcotics prescribed. This is based on evidence suggesting a direct relationship between use of postoperative narcotics in opioid naïve patients and increased risk of continued use in 1 year. In light of the CDC guidelines, alternative means to reduce patient pain and narcotic use after hysterectomy are clinically relevant. In addition, documenting narcotic use patterns after hospital discharge following hysterectomy is vital to understand appropriate prescribing practices.

The use of postoperative cooling for pain has previously been shown to be effective in a variety of procedures, including laparotomy, inguinal hernia repair, total knee arthroplasty, craniotomy, oral surgery, and tonsillectomy, but has yet to be described for laparoscopic surgery. Safety in regards to surgical site infection (SSI) is evidenced by the routine use of postoperative ice packs in orthopedic surgery based on a robust literature demonstrating no increased rate of SSIs in total-knee arthroplasty with hardware placement or anterior cruciate ligament repair procedures. Abdominal ice packs placed continuously for 24 hours after laparotomy in one study resulted in both decreased pain scores and reduced use of narcotics during the 24 hour time period, with no incidence of hypothermia.

The primary investigator routinely uses abdominal ice packs following laparoscopic hysterectomy and has observed beneficial effects on pain reduction. In contrast to laparotomy where the wound is a significant pain generator and direct application of ice is intuitive, in laparoscopic surgery much of the pain-generating tissue trauma is intraperitoneal and pelvic in nature, away from the abdominal wall. A plausible mechanism for pain inhibition with abdominal placement of ice packs in this scenario may be found in abdominopelvic neuroanatomy. Cross-talk between neuro pathways has been used to describe referred pain to the abdominal wall via somatic nerve distributions despite originating from visceral afferents. Pain from visceral afferent nerves traveling through the dorsal horn of the spinal cord come in close association with poorly myelinated somatic afferents, causing cross-talk to occur and referred pain in the corresponding dermatome. This viscerosomatic convergence is reported between the ovaries/distal fallopian tubes and the iliohypogastric nerve, the proximal fallopian tubes/uterine fundus and the ilioinguinal/genitofemoral nerves, and the uterine fundus/lower uterine segment and

Abdominal ice packs for pain control and reduction of narcotic use following laparoscopic hysterectomy: a randomized controlled trial. [name].

the lateral femoral cutaneous nerve. The reverse pathway, pain from the somatic afferents referring to the pelvic visceral afferents, has also been described. Accordingly, applying ice to the abdominal wall and its somatic afferents may indeed have the ability to interfere in some fashion with pain signals originating from the pelvic visceral afferents and improve laparoscopic pain control despite the lack of a significant abdominal wound.

### **Hypothesis**

The use of abdominal ice packs following laparoscopic hysterectomy will result in improved pain control and reduction in narcotic consumption compared to patients not using ice packs.

### **Specific Aims**

1. Document average patient morphine metabolic equivalents (MME) consumption after laparoscopic hysterectomy from hospital discharge to narcotic self-discontinuation.
2. Evaluate the effect of abdominal ice packs vs routine care on total (MMEs) consumed by patients during the perioperative and entire postoperative period.
3. Evaluate the effect of abdominal ice packs vs routine care on validated pain measures during the first 12 hours after surgery.

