### **Research Plan and Methods**

Patients  $\geq 18$  years old undergoing laparoscopic (either conventional or robotic) hysterectomy will be recruited. Patients will be excluded for (a) taking opioid analgesics, including Tramadol, on a daily basis within the two weeks prior to surgery (b) planned ICU admission identified prior to randomization, (c) conversion to laparotomy or any incision  $\geq 4$  cm, (d) regional anesthesia or tap block use, and (e) planned same-day discharge. The intent of excluding patients who are opioid tolerant, defined as patients who are chronically receiving opioid analgesics on a daily basis, is to prevent confounding of our specific aims related to total opioid use. Patients will not be excluded due to additional surgical procedures performed or due to malignancy as an indication for surgery. Trial will adhere to CONSORT guidelines.

In the preoperative area, the Brief Pain Inventory-short form (BPI) will be administered by study personnel, as the first of two questionnaires. The BPI short form is a validated measure that will allow for quick assessment of baseline and postoperative pain severity and impact on function. Preoperative and intraoperative medications will be standardized using a modified Magic Pathway (multimodal analgesia) with intraoperative narcotic guidelines. All intraoperative and postoperative pain management decisions will be left to the discretion of the subject's surgeon. Following incision closure, the surgeon will determine eligibility for randomization. Subjects will be randomized, using REDcap, by a study coordinator to abdominal ice pack plus routine care or routine Randomization will be stratified into two groups, patients with chronic pelvic pain (pain present for  $\geq 6$  months, excluding isolated dysmenorrhea) and patients without chronic pelvic pain; there will be no stratification for surgical approach. Blinding will not be possible for patients, physicians, or study coordinator.

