Demographics (i.e., age, gravida, para, BMI) and intraoperative statistics will be documented (surgical time, blood loss, uterine weight, additional procedures, intraoperative complications, use of pre- and/or post-incision local analgesia). During postoperative admission, arrival time to PACU, lowest recorded temperature, pain scores (arrival to PACU, last pain score in PACU, and all inpatient pain scores through 12 hours), and immediate complications will be recorded. Inpatient pain scores will be abstracted from the medical record nurse charting, which per protocol are at minimum every 4 hours.

After between 12 and 24 hours or at hospital discharge (whichever occurs first), subjects will be administered a second survey, reflecting a compilation of the following tools. The ice group will be asked to complete the BPI short form, the Overall Benefit of Analgesia Score (OBAS) measure, and answer questions assessing ice pack tolerability, satisfaction with pain control, and perceived adherence to use (% of time ice pack perceived to be on abdomen during first 12 h). Routine care patients will only complete the BPI short form and OBAS. The OBAS is a 7-item, validated tool specifically designed for post-operative assessment of pain, side effects and satisfaction with analgesia within the first 24 hours following surgery.

MMEs will be recorded in split timeframes: starting from subject arrival at PACU to discharge from PACU; arrival to floor until 12 hours s/p surgery; 12 hours s/p surgery until hospital discharge; and from hospital discharge to self-discontinuation. Hospital charts will be used to obtain MMEs while subjects are admitted. Subjects will be instructed to keep unused narcotic medication and bring it with them for accurate use counts at the scheduled post-operative visit, typically six weeks following dismissal. A medication/pain diary will be kept by patients after discharge to include pain scores and all narcotic-type medications consumed, including those not prescribed for the current surgery. The diary will be kept daily until the last dose of narcotic pain medication is needed. Subjects in the treatment arm will additionally record duration of ice pack use during the first 24 hours after hospital discharge. This measure will be incorporated into the diary for ease of completion.

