### **Statistics**

Descriptive statistics will be applied to demographics, intraoperative, and postoperative data. Comparisons between groups will be performed using a 2-tailed *t*-test or Mann-Whitney U for parametric and non-parametric data as appropriate. A *p*-value of 0.05 will be used to determine statistical significance.

Primary analysis will be an intention-to-treat analysis of total MME use after surgery. Secondary analyses will evaluate effect on pain scores, patient satisfaction with pain control,

No previously published data on narcotic consumption after discharge for any minimally invasive hysterectomy (vaginal, laparoscopic, robotic) could be identified in a literature search. Chart review averaging 3 patients' data demonstrated average use of 150 MMEs after laparoscopic hysterectomy from PACU admission to hospital discharge. Assuming use of 20 oxycodone 5 mg tablets following discharge yields an additional 150 MMEs; total estimated use after laparoscopic hysterectomy is 300 MMEs. Considering a 20% MME reduction as clinically significant (8 x 5mg oxycodone pills), an alpha of 0.05, power of 90%, and SD of 100 MMEs with a 1:1 sampling ratio, 59 subjects per arm (total 118) would be required to demonstrate a statistically significant difference. Addition of a 20% margin for losses to follow up, pre- and post-randomization exclusions, 142 patients would be targeted for recruitment.

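### The primary MME comparison is unadjusted despite stratified randomization, pre-randomization intraoperative opioid is not a listed data item, and Aim 2 names a wider window than is recorded

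*Combined protocol and SAP*

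**What the plan says.** All references are to the combined protocol and SAP.

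- **Specific Aims, Aim 2:** the effect of ice is to be evaluated on total MMEs "consumed by patients during the perioperative and entire postoperative period".
- **Research Plan and Methods, MME recording:** "MMEs will be recorded in split timeframes: starting from subject arrival at PACU to discharge from PACU". The remaining windows are "arrival to floor until 12 hours s/p surgery; 12 hours s/p surgery until hospital discharge; and from hospital discharge to self-discontinuation". For the inpatient part, "Hospital charts will be used to obtain MMEs while subjects are admitted".
- **Research Plan and Methods, data items:** "intraoperative statistics will be documented (surgical time, blood loss, uterine weight, additional procedures, intraoperative complications, use of pre- and/or post-incision local analgesia". Systemic opioid dose is not listed.
- **Research Plan and Methods, randomization:** "Following incision closure, the surgeon will determine eligibility for randomization". Allocation is stratified by presence or absence of chronic pelvic pain. Preoperative and intraoperative drugs are standardized with narcotic guidelines, but intraoperative pain decisions remain with the surgeon.
- **Statistics:** "Primary analysis will be an intention-to-treat analysis of total MME use after surgery". Groups are compared by a two-tailed t-test or Mann-Whitney U. Neither the stratum nor any covariate is mentioned. The 150 MME inpatient planning figure also starts at PACU admission.

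**The concern.** Three features do not fit together.

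1. Aim 2 names the perioperative period in addition to the whole postoperative period, so it appears to cover opioid given in theatre. No recording window does. The term is not defined, so two people reporting the trial could start the total at different points.
2. The design stratifies on chronic pelvic pain, presumably because it is expected to predict opioid use, and the analysis then ignores it. Stratified allocation balances the arms on that factor. If the factor predicts MME, an unadjusted test still counts the between-stratum variation as error, so the standard error is larger than it need be.
3. Intraoperative opioid is fixed before allocation and could plausibly predict early postoperative need. As it is not a listed item, it can be neither used as a covariate nor tabulated to show whether the arms were alike at PACU arrival.

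At stake are some precision in the primary comparison and a clear definition of the primary outcome. Validity is not in question.

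**Working it through.** **1. The windows side by side**

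| Place | Start of MME window |
|---|---|
| Aim 2 | Perioperative, undefined |
| MME recording | PACU arrival |
| Primary analysis | After surgery |
| 150 MME planning figure | PACU admission |

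The three operational statements are compatible with one window; only Aim 2 is wider. Ice is placed before the patient leaves the operating room, after randomization. It therefore cannot affect opioid given before allocation, and the between-arm difference from PACU onward answers Aim 2's comparative question. The exception is opioid given between randomization and PACU arrival, which falls in no window.

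**2. The plan's own sample size**

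Inputs from Statistics: total 300 MME, 20% reduction, SD 100, two-sided alpha 0.05, power 90%, 1:1 allocation.

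- Difference = 0.20 × 300 = 60 MME.
- n per arm = 2 × (1.960 + 1.282)² × 100² / 60² = 58.4, rounded up to 59, or 118 in total. This reproduces the plan's figure.
- Power at 59 per arm is 90.3% by the normal approximation and 89.8% by the t distribution. The t-based requirement is 59.35, that is 60 per arm.

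The calculation already uses the PACU-onward window, so rewording Aim 2 does not alter it.

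**3. Adjusting for intraoperative opioid**

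The documents give no correlation r between intraoperative MME and total postoperative MME, so r is an assumed range. Residual SD = 100 × √(1 − r²). The equivalent gain in patients is 1/(1 − r²) − 1.

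| r (assumed) | Residual SD | Power at 59 per arm, normal | Power, t | n per arm for 90%, normal | Equivalent gain |
|---|---|---|---|---|---|
| 0 | 100.0 | 90.3% | 89.8% | 59 | 0 |
| 0.1 | 99.5 | 90.6% | 90.1% | 58 | 1.0% |
| 0.2 | 98.0 | 91.4% | 91.0% | 57 | 4.2% |
| 0.3 | 95.4 | 92.7% | 92.3% | 54 | 9.9% |
| 0.4 | 91.7 | 94.5% | 94.1% | 50 | 19.0% |

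**4. Why the gain may be smaller**

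Half of the planned 300 MME is post-discharge tablets. Suppose intraoperative dose predicts only the inpatient half, and the two halves have equal, independent variance (an assumption). Then r with the total is the inpatient r divided by √2. An inpatient r of 0.2 to 0.4 becomes 0.14 to 0.28, and t-based power is 90.4% to 92.1%.

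**5. Adjusting for the stratum**

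The same formula applies, with r² the share of MME variance explained by chronic pelvic pain. The documents give neither the prevalence of chronic pelvic pain nor its effect on MME, so no figure can be attached. The expected gain is about nil if the factor does not predict MME and positive if it does.

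**The case against.** The strongest case against is that an unadjusted t-test or Mann-Whitney U is valid under randomization, with chance imbalance already covered by the type I error rate. The operational parts of the plan agree on one window. Medications are standardized, which may narrow the spread of intraoperative dose, and surgical time, additional procedures and local analgesia are already collected. All of this stands. It limits the size of the point, but it shows no drawback to a prespecified adjusted analysis.

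Four stronger readings are tempting, and the documents do not support them.

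- *A reader might infer that Aim 2 cannot be answered.* The between-arm effect can be estimated from PACU onward. What cannot be computed is an absolute total that includes theatre opioid, together with any dose given between randomization and PACU arrival.
- *A reader might infer that a strong covariate is being discarded.* No correlation is given, so nothing supports calling it strong.
- *A reader might infer that the information is lost.* The dose should be retrievable from the anesthesia record, and inpatient MMEs already come from hospital charts. It is simply not a planned item.
- *A reader might infer a material loss of power from adding theatre opioid to the outcome.* With an assumed intraoperative SD of 40 and r of 0.3, the total SD would be √(10,000 + 1,600 + 2,400) = 118.3 and t-based power 78.0%. But no part of the recording or analysis plan adds it, and the direction depends on the assumed sign. With r of −0.3 and SD 20, the total SD is √(10,000 + 400 − 1,200) = 95.9, below 100.

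**Conclusion.** The point holds in a limited form. The Aim 2 wording is inconsistent with the recording windows and the primary analysis and should be clarified, but it affects no stated figure and does not prevent estimation of the treatment effect. The improvement worth making is to the primary analysis: it should reflect the stratified randomization, and it could use intraoperative opioid as a baseline covariate.

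The benefit of the stratum adjustment cannot be quantified from the documents. The benefit of the opioid covariate rests wholly on an assumed correlation. At 0.2 to 0.4, power rises by roughly 1 to 4 percentage points from about 90%. Below 0.2 the gain is negligible, and standardized medication may well put it there. The case for acting is that the changes cost almost nothing, not that the current analysis is invalid.

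**What to change.** 1. **Outcome definition.** In Specific Aims and Statistics, define the primary outcome as total MME from PACU arrival to self-discontinuation of narcotics, and remove or define the perioperative term in Aim 2. State that opioid given before randomization is not part of the outcome. Cost: wording only.
2. **Primary analysis.** Replace the unadjusted comparison with a prespecified linear model of total MME on treatment arm and chronic pelvic pain stratum. State in advance how skewness will be handled, for example by a named transformation or a stratified rank test. Cost: none, since the stratum is known at randomization.
3. **Baseline opioid.** Add intraoperative MME to the intraoperative data list, abstracted from the anesthesia record, and prespecify it as a covariate. Count only doses given before randomization, and record separately any given between randomization and PACU arrival, because those are post-allocation. Cost: one extra abstracted field, with the dose times needed to split it.

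No change to the sample size follows from this point. The unadjusted comparison can be kept as a sensitivity analysis.

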### **Is the Research aiming to answer to an unmet need of the patient (either a specific clinical need or patient satisfaction)? If yes, please explain in detail.**

Yes. Reducing postoperative pain and reducing postoperative narcotic use are unmet needs of the patient. Current postop pain regimens for laparoscopic surgery depend heavily on narcotic and non-narcotic medications, thus there is a need for low-cost non-medication alternatives. Furthermore, reducing narcotic use postoperatively may also reduce the risk of future narcotic dependence, which lies at the core of this unmet need.

### **Research Plan and Methods**

Patients  $\geq 18$  years old undergoing laparoscopic (either conventional or robotic) hysterectomy will be recruited. Patients will be excluded for (a) taking opioid analgesics, including Tramadol, on a daily basis within the two weeks prior to surgery (b) planned ICU admission identified prior to randomization, (c) conversion to laparotomy or any incision  $\geq 4$  cm, (d) regional anesthesia or tap block use, and (e) planned same-day discharge. The intent of excluding patients who are opioid tolerant, defined as patients who are chronically receiving opioid analgesics on a daily basis, is to prevent confounding of our specific aims related to total opioid use. Patients will not be excluded due to additional surgical procedures performed or due to malignancy as an indication for surgery. Trial will adhere to CONSORT guidelines.

In the preoperative area, the Brief Pain Inventory-short form (BPI) will be administered by study personnel, as the first of two questionnaires. The BPI short form is a validated measure that will allow for quick assessment of baseline and postoperative pain severity and impact on function. Preoperative and intraoperative medications will be standardized using a modified Magic Pathway (multimodal analgesia) with intraoperative narcotic guidelines. All intraoperative and postoperative pain management decisions will be left to the discretion of the subject's surgeon. Following incision closure, the surgeon will determine eligibility for randomization. Subjects will be randomized, using REDcap, by a study coordinator to abdominal ice pack plus routine care or routine Randomization will be stratified into two groups, patients with chronic pelvic pain (pain present for  $\geq 6$  months, excluding isolated dysmenorrhea) and patients without chronic pelvic pain; there will be no stratification for surgical approach. Blinding will not be possible for patients, physicians, or study coordinator.

A large zip lock bag (size standardized) full of ice chips, placed inside a pillow case, will be placed directly on the abdomen prior to leaving the operating room, for subjects randomized to ice therapy. Ice will be kept on the abdomen continuously for the first 12 hours, however patients will be allowed to remove and replace ice as desired for comfort. Bag will be refilled with ice by hospital staff as needed, and patient will carry the bag home for continued use after discharge. Patient will be encouraged to continue using ice pack through 24 hours and beyond if found to be helpful.

Safety will be carefully monitored in ice pack subjects. Ice packs will always be placed on the abdomen wrapped within a pillow case to reduce the risk of cold burns from ice being directly on the skin. Subjects may remove the ice at any time if discomfort is experienced, limiting the risk of frost bite. Unit nurse will check skin at minimum every 4 hours, and evaluate per the current Nursing Procedural Guideline: Ice Pack Use (immediate removal if skin appears mottled, gray, macerated, blistered, and/or if patient reports extreme burning or numbness). Any skin changes at subject discharge will be recorded as adverse events and prompt a protocol safety review if determined to be secondary to ice pack use (as opposed to skin prep,

Abdominal ice packs for pain control and reduction of narcotic use following laparoscopic hysterectomy: a randomized controlled trial.  
[name].

bandages, etc.). Safety of a continuous use protocol has previously been demonstrated by Watkins et al, where continuous ice packs were used against an abdominal incision for 24 hours in 27 patients with zero patients experiencing thermal injury. Anecdotally, the primary investigator has been using continuous ice packs as described in this protocol for all laparoscopic hysterectomy patients since mid-2016; conservatively, over 90 patients during that time have used ice packs, with zero thermal injuries noted (the primary investigator personally sees and examines all of his patients on postoperative day 1, after 12-24 hours of ice pack use).

Demographics (i.e., age, gravida, para, BMI) and intraoperative statistics will be documented (surgical time, blood loss, uterine weight, additional procedures, intraoperative complications, use of pre- and/or post-incision local analgesia). During postoperative admission, arrival time to PACU, lowest recorded temperature, pain scores (arrival to PACU, last pain score in PACU, and all inpatient pain scores through 12 hours), and immediate complications will be recorded. Inpatient pain scores will be abstracted from the medical record nurse charting, which per protocol are at minimum every 4 hours.

After between 12 and 24 hours or at hospital discharge (whichever occurs first), subjects will be administered a second survey, reflecting a compilation of the following tools. The ice group will be asked to complete the BPI short form, the Overall Benefit of Analgesia Score (OBAS) measure, and answer questions assessing ice pack tolerability, satisfaction with pain control, and perceived adherence to use (% of time ice pack perceived to be on abdomen during first 12 h). Routine care patients will only complete the BPI short form and OBAS. The OBAS is a 7-item, validated tool specifically designed for post-operative assessment of pain, side effects and satisfaction with analgesia within the first 24 hours following surgery.

MMEs will be recorded in split timeframes: starting from subject arrival at PACU to discharge from PACU; arrival to floor until 12 hours s/p surgery; 12 hours s/p surgery until hospital discharge; and from hospital discharge to self-discontinuation. Hospital charts will be used to obtain MMEs while subjects are admitted. Subjects will be instructed to keep unused narcotic medication and bring it with them for accurate use counts at the scheduled post-operative visit, typically six weeks following dismissal. A medication/pain diary will be kept by patients after discharge to include pain scores and all narcotic-type medications consumed, including those not prescribed for the current surgery. The diary will be kept daily until the last dose of narcotic pain medication is needed. Subjects in the treatment arm will additionally record duration of ice pack use during the first 24 hours after hospital discharge. This measure will be incorporated into the diary for ease of completion.

At the scheduled postoperative visit, pill counts will be completed, medication/pain diary collected, and 30-day postoperative complications (surgical site infections, readmissions, etc.) assessed. If patients do not return to Mayo Clinic for a postop exam, a prepaid envelope will be sent to have diary returned by mail and complications/readmissions and pill count assessed by phone with the study coordinator.

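### Operating surgeon is neither listed for recording nor used in the analysis, so between-surgeon variation in opioid use stays in the error term and dependence on the primary investigator's patients goes unexamined

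*Combined protocol and SAP*

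**What the plan says.** Research Plan and Methods names one stratification factor: "Randomization will be stratified into two groups, patients with chronic pelvic pain" and patients without it. It adds that "there will be no stratification for surgical approach". The operating surgeon is not mentioned either way.

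On analgesia the same section says "Preoperative and intraoperative medications will be standardized using a modified Magic Pathway (multimodal analgesia) with intraoperative narcotic guidelines", and then "All intraoperative and postoperative pain management decisions will be left to the discretion of the subject's surgeon". Patients enter late: "Following incision closure, the surgeon will determine eligibility for randomization". Nobody involved is blinded.

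On the primary investigator's own practice it says "the primary investigator has been using continuous ice packs as described in this protocol for all laparoscopic hysterectomy patients since mid-2016". The Background adds that this investigator has seen a benefit on pain.

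The listed intraoperative data are "surgical time, blood loss, uterine weight, additional procedures, intraoperative complications, use of pre- and/or post-incision local analgesia". Surgeon is absent there and from the demographic and postoperative lists. Inpatient MMEs and pain scores come from each subject's chart.

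The Statistics section plans a two-sided t-test or Mann-Whitney test on total MME by intention to treat, with no covariate. It assumes a mean of 300 MME, an SD of 100, a 20% reduction, 90% power and 59 subjects per arm.

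**The concern.** Total MME partly reflects what the surgeon orders. Counting starts on arrival at PACU, after the phase in which medication is standardised. The Timeline section gives 586 laparoscopic or robotic hysterectomies in 2016, so more than one operator is a safe inference, although the number is not stated. One operator is known to differ: for the primary investigator's patients, the control arm withholds what has been routine.

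Two things are at stake. Any part of the MME variance that lies between surgeons stays in the residual when it could be taken out. And the Innovation section expects a positive result to be taken up widely, yet no planned analysis shows whether the effect holds in patients of surgeons without a prior commitment to ice.

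**Working it through.** **1. The plan's own figure.** The difference is 20% of 300 = 60 MME, with SD 100, two-sided alpha 0.05 and power 90%.
- n per arm = 2 × (1.960 + 1.282)² × 100² / 60² = 58.4, rounded up to 59. The stated 59 per arm (118 in all) reproduces.
- The SE of the difference at 59 per arm is 100 × √(2/59) = 18.4 MME. Power is 90.3% by the normal approximation and 89.8% by the exact t-test. The t-test figure is the baseline in steps 3 and 4.

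**2. Type I error.** The documents give neither the number of surgeons nor the variance between them. A simulation used 118 patients, 6 or 12 assumed surgeons, 5% to 20% of variance between surgeons, unstratified 1:1 allocation and 3,000 runs per scenario. The unadjusted t-test rejected in 4.6% to 5.6% of null runs, with a Monte Carlo SE of about 0.4 points. There is no material inflation.

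**3. Adjusting for primary investigator versus other.** Two inputs are assumed: the primary investigator's share p of the sample (10% to 40%) and a 60 MME gap from other surgeons' patients. SD 100 is taken as the total SD. The factor explains p(1 − p) × 60² / 100² of the variance.

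| p | Share explained | Residual SD | Power at 59 per arm |
|---|---|---|---|
| 10% | 0.09 × 3,600 / 10,000 = 3.2% | 98.4 | 90.7% |
| 40% | 0.24 × 3,600 / 10,000 = 8.6% | 95.6 | 92.2% |

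The documents anchor only the low end of p. They report over 90 ice patients since mid-2016. Assuming about 20 months (a reference was accessed in February 2018), that is 90 / 20 × 12 = 54 a year, or 9% of 586. It is a floor, and a share of caseload rather than of enrolment.

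**4. Ceiling if every surgeon is modelled.** With an assumed between-surgeon share of 5%, 10% or 20%, the SD falls to 97.5, 94.9 or 89.4 and power rises to at most 91.2%, 92.6% or 95.1%. In simulation, with surgeon as a fixed effect and no stratification, power was 90%, 91% and 94% with 6 surgeons and 88%, 91% and 93% with 12. When the share is small, many surgeon terms cost as much as they return.

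**5. If SD 100 leaves surgeon variation out.** The source of the SD is not stated. At the same three shares the total SD would be 102.6, 105.4 or 111.8. Unadjusted power would be 88.8%, 87.1% or 83.0% (normal approximation), and 62, 65 or 73 per arm would be needed.

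**6. Leaving out the primary investigator's patients.**
- At p = 10%, 59 × 0.9 = 53 per arm remain. With SD 98.4, power is 87.5% and the 95% interval is about ±37 MME.
- At p = 40%, 59 × 0.6 = 35 per arm remain. With SD 95.6, power is 73.5% and the interval is about ±45 MME.
- The full sample at SD 100 gives ±36 MME.

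**The case against.** A reader might infer that operator effects can never be removed. The documents do not support that. Inpatient data come from each subject's chart, which very likely identifies the operator, so surgeon could still be added before analysis. The plan simply does not provide for it.

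A reader might also infer bias from a chance imbalance in surgeon mix. On the step 3 assumptions, the SE of the between-arm difference in share is √(p(1 − p) × 2/59), or 5.5 to 9.0 points. A two-SE imbalance therefore moves the estimate by 6.6 to 10.8 MME. But patients are randomised individually, and this movement is already inside the SE of 18.4 MME and so inside the p-value. It is not an extra error.

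Other objections stand in part:
- If SD 100 is the total SD, planned power is met without adjustment. The gain is then power above target, not repair of a shortfall.
- Half of the assumed 300 MME is taken by patients at home until they stop, so surgeons' orders act only partly on the endpoint.
- The choice of strata is a design judgement. With a stratum for primary investigator versus other and the unadjusted test kept, simulated power was 90.5% to 90.7%, against 89.8% to 90.2% without it (40,000 runs). That is practically no gain.
- An unblinded surgeon who favours ice may prescribe differently by arm, or control patients may get ice. Neither stratification nor adjustment removes this.

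What remains is that the plan neither lists surgeon nor uses it, and that doing both is nearly free.

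**Conclusion.** The point holds as a cheap improvement. As written, between-surgeon variation will not be removed from total MME, and dependence of the result on the primary investigator's patients will not be examined. The loss is one of precision and interpretability. Type I error is unaffected, and surgeon mix does not bias the comparison in expectation.

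The two-level adjustment is worth one to two points of power, from about 90% to 91-92%, if the primary investigator's patients are 10% to 40% of the sample and differ by 60 MME. Both inputs are assumptions. A gain to 95% might be inferred from the ceiling in step 4, but a two-level factor does not reach it on these inputs. The larger benefit is interpretive: in an unblinded trial, readers could see whether the finding rests on one surgeon who already uses ice routinely.

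**What to change.** 1. Record the operating surgeon, from the operative record, for every randomised patient.
2. Pre-specify an analysis of total MME adjusted for surgeon (at least primary investigator versus other) and for the chronic pelvic pain stratum.
3. Pre-specify a sensitivity analysis that leaves out the primary investigator's patients. Report it as an estimate with a confidence interval, not as a second significance test.
4. Treat an added randomisation stratum for primary investigator versus other as optional. A stratum for every surgeon crossed with pelvic pain would risk sparse cells in 118 patients.
5. Reconcile the statement that intraoperative medication is standardised with the one leaving intraoperative pain decisions to the surgeon, so that it is clear where surgeons can differ.

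The cost is one extra field, one model and one less precise table. None of this addresses prescribing that differs by arm among unblinded surgeons, and the report should say so.
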